- Serum transaminases (alanine aminotransferase [ALT] and/or aspartate aminotransferase [AST]) > 3 x upper limit of normal (ULN) AND total bilirubin > 2 x ULN (confirmed by subsequent repeat).
- ALT or AST > 3 x ULN (confirmed by repeat visit) with the appearance or worsening of symptoms felt by the Investigator to be potentially related to hepatic inflammation, such as fatigue, nausea, vomiting, right upper quadrant pain or tenderness, fever, rash, or eosinophilia.
- QTcF > 500 ms or increase > 60 ms from time matched baseline (confirmed by repeat

ECG).

- Occurrence of an exclusion criterion which is clinically relevant and affects the patient's safety, if discontinuation is considered necessary by the Principal Investigator and/or Sponsor.

In order to perform the modified intention to treat (mITT) analysis, and to enable safety analyses, all patients who discontinue their medication will be asked to still complete their follow-up visit (Visit 6) as outlined in the study schedule.

Patients who withdraw from the study will not be replaced.

In all cases, the reason(s) for withdrawal must be recorded on the electronic CRF (eCRF).

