## 7.7 12-lead Electrocardiograms (ECG)

A 12-lead ECG will be performed at all clinic visits. 12-lead serial ECGs will be recorded at Visit 2 (Enrolment) pre-dosing and after 30 minutes, 1 hour and 2 hours post-dosing ( $\pm 10$  minutes).

On dosing days, ECG should be performed 30 minutes after dosing ( $\pm 10$  minutes).

The 12-lead ECG will be performed after the patient has been resting in a supine position for at least 10 minutes.

All ECGs will be assessed by the investigator, and the data will be recorded in the eCRF. The clinical significance of ECG results will be determined by the investigator after review of the ECG report in relation to the patient's medical history, physical examination findings, and concomitant medications.

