Final 1.0
16 January 2018

Abbreviations: AE=Adverse event; anti-HBc=Total Hepatitis B core antibody; anti-HBs= Antibody to Hepatitis B surface antigen; ECG=Electrocardiogram; eCRF=Electronic case report form; EQ-5D-5L=EQ-5D is a standard measure of health status developed by the EuroQol Group in order to provide a simple, generic measure of health for clinical and economic appraisal; HBsAg=Hepatitis B surface antigen; HCV=Hepatitis C virus; HIV=Human immunodeficiency virus; ICOAP=Intermittent and constant osteoarthritis pain; IMP=Investigation medicinal product; K-L=Kellgren and Lawrence; MRI=Magnetic resonance imaging; NRS=Numeric rating scale; PK=pharmacokinetic(s); PRO=Patient reported outcomes; SAE=Serious adverse event; WOMAC=Western Ontario and McMaster Universities Osteoarthritis Index.

- A. Selection of target knee was to be primarily based on pain, secondarily on K-L Grade, and if both sides were equal with regard to these two criteria, the right knee was always to be prioritised.
- B. Targeted physical examination. Full physical examination at all other visits.
- C. At Visit 2 at pre-dosing, 0.5, 1 and 2 hours post-dosing (\pm 10 minutes). At all other visits 30 minutes post-dose (\pm 10 minutes).
- D. If urinalysis was positive for blood, nitrites, leukocyte esterase, and/or protein, additional microscopic analysis was to be performed.
- E. MRI was to be performed at Visit 2 (-7 days) and at Visit 8 (\pm 5 days).
- F. To be completed at home during the 2 weeks prior to the marked visit.
- G. Only NRS for average overall knee pain severity (1-week recall) for both knees.
- H. The first dose of IMP was to be dispensed to the patient at the site. Date and time was to be recorded in the eCRF. The first dose was to be given to the patient after all baseline assessments had been performed including completion of Patient Reported Outcomes (PROs). Patients were to take the IMP in the clinic in a fasting state and were required to stay at the clinic for 2 hours after intake of the IMP.
- I. Patients were to take the IMP in the clinic in a fasting state. Breakfast was to be eaten 1 hour after IMP intake. The last dose of the IMP was to be taken at the site during Visit 8.
- J. Both blood and urine samples were to be collected for biomarker. The first void of morning urine must have occurred before the urine sample was taken from a later void. The patients were to be fasting when all biomarker samples were taken.

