4.6.3 Safety Analysis Population (SAF)

The safety analysis population will be the same as the ITT population.

5. Protocol Deviations

Deviations from the protocol including violations of inclusion/exclusion criteria will be assessed as “minor” or “major” in cooperation with the sponsor. Major deviations from the protocol will lead to the exclusion of a patient from the Per Protocol Set (PPS). Deviations will be defined prior to data base hard lock.

The following criteria will be used to exclude a patient from an analysis set:

- Incorrect diagnosis
- Any of the prohibited interventions/injuries for the target knee
- Missing more than 7 doses of MIV-711
- Discontinuation from the study

Note: this is not an exhaustive list of deviations, these are only the deviations specified per protocol. The discussion during the data review meeting post data base soft lock will review all deviations collected at each site and it will be decided to which analysis set each patient belongs.

6. General Considerations for Data Presentations

In this study IMP refers to any amount of the treatments defined in section 3.5, regardless of the time or period of administration.

Data for all patients enrolled in study MIV-711-202 who receives at least one dose of IMP will be presented in the data listings.

PAREXEL International Statistical Analysis Plan

Medivir
Protocol: MIV-711-202

Final 1.0
16 January 2018

A patient who is enrolled in study MIV-711-202 but does not receive IMP will be included in those data listings for which they have data but will be excluded from all data summaries. Data summaries will only include those patients that receive IMP.

For those listings or data summaries where baseline and change from baseline measurements will be presented, unless stated otherwise, the baseline assessment to be used for calculating change from baseline will be the last valid assessment prior to first dose of 200 mg MIV-711. Note that the change from baseline will be calculated also for visits prior to the baseline visit, not only for visits succeeding the baseline visit.

Data from both studies for patients enrolled in study MIV-711-202 will be included in the data listings, tables and figures, as appropriate.

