8.3.9 Brief Medication Questionnaire

Brief medication questionnaire results will be summarized for the number and percentage of patients reporting:

- each medication taken
- each indication
- combination of medication taken per indication
- compliance for each medication taken

Descriptive summary tables will be presented separately for Group A and Group B. Summary tables and listings for brief medication questionnaire will only be based on data from MIV-711-202 study.

9. Safety Analysis

For the safety outcomes, for study Group A, changes from baseline will be assessed using the Visit 2 baseline data from MIV-711-201. For study Group B, changes from baseline will be assessed using the Visit 2 data from Study MIV-711-202.

The change from baseline for visit X will be calculated as the (visit X – baseline visit)-difference in observed values. Note that the change from baseline will be calculated for all visits in study MIV-711-201 and study MIV-711-202 where the actual endpoint has been observed, i.e. not only for visits in study MIV-711-202 succeeding the baseline visit.

All safety summary tables will be based on the SAF population.

Descriptive summaries for safety will be presented by study group and visit, as appropriate.

PAREXEL International Statistical Analysis Plan

Medivir
Protocol: MIV-711-202

Final 1.0
16 January 2018

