VISIT 2	n	nn		nn	nn
MIV-711-201	Mean	xx.x		xx.x	xx.x
DAY 1	SD	xx.xx		xx.xx	xx.xx
	Median	xx.x		xx.x	xx.x
	Min	xx		xx	xx
	Max	xx		xx	xx
VISIT 3	n	nn	nn	nn	nn
MIV-711-201	Mean	xx.x	xx.x	xx.x	xx.x
WEEK 2	SD	xx.xx	xx.xx	xx.xx	xx.xx
	Median	xx.x	xx.x	xx.x	xx.x
	Min	xx	xx	xx	xx
	Max	xx	xx	xx	xx
Visit 4	n	nn	nn	nn	nn
MIV- 711-201	Mean	xx.x	xx.x	xx.x	xx.x
WEEK 3	SD	xx.xx	xx.xx	xx.xx	xx.xx
	Median	xx.x	xx.x	xx.x	xx.x
	Min	xx	xx	xx	xx
	Max	xx	xx	xx	xx
Etc...					

Baseline is defined as: Visit 2 in the MIV-711-201 for Group A, Visit 2 in the MIV-711-202 for Group B
QTcB = QT corrected according to Bazett, QTcF = QT corrected according to Fridericia.

PAREXEL International SAP Amendment Shells

Medivir
Protocol: MIV-711-202

Final 1.0
16 January 2018

Medivir
Protocol Number: MIV-711-202

Page X of Y

Table 14.3.4.2
12 Lead ECG - Categorical Summary of Observed Values
SAF Population

Parameter = QT (msec)

Visit	Category (unit)	Group A N = x	Group B N = x
VISIT 1	≤ 450	nn (nn.n%)	nn (nn.n%)
MIV-711-201	450 < to ≤ 480	nn (nn.n%)	nn (nn.n%)
SCREENING	480 < to ≤ 500	nn (nn.n%)	nn (nn.n%)
	>500	nn (nn.n%)	nn (nn.n%)
VISIT 2	≤ 450	nn (nn.n%)	nn (nn.n%)
MIV-711-201	450 < to ≤ 480	nn (nn.n%)	nn (nn.n%)
DAY 1	480 < to ≤ 500	nn (nn.n%)	nn (nn.n%)
	>500	nn (nn.n%)	nn (nn.n%)
VISIT 3	≤ 450	nn (nn.n%)	nn (nn.n%)
MIV-711-201	450 < to ≤ 480	nn (nn.n%)	nn (nn.n%)
WEEK 2	480 < to ≤ 500	nn (nn.n%)	nn (nn.n%)
Etc...	>500	nn (nn.n%)	nn (nn.n%)

Baseline is defined as: Baseline is defined as: Visit 2 in the MIV-711-201 for Group A, Visit 2 in the MIV-711-202 for Group B

QTcB = QT corrected according to Bazett, QTcF = QT corrected according to Fridericia.

Programming note: Table will include: QTcB interval and QTcF interval

PAREXEL International SAP Amendment Shells

Medivir
Protocol: MIV-711-202

Final 1.0
16 January 2018

Medivir
Protocol Number: MIV-711-202

Page X of Y

Table 14.3.4.3
12 Lead ECG - Categorical Summary of Change from Baseline
SAF Population

Parameter = QT (msec)

Visit	Category (unit)	Group A N = x	Group B N = x
VISIT 1	<= 0	nn (nn.n%)	nn (nn.n%)
MIV-711-201	>0 to ≤ 30	nn (nn.n%)	nn (nn.n%)
SCREENING	>30 to ≤ 60	nn (nn.n%)	nn (nn.n%)
	>60	nn (nn.n%)	nn (nn.n%)
VISIT 2	<= 0	nn (nn.n%)	nn (nn.n%)
MIV-711-201	>0 to ≤ 30	nn (nn.n%)	nn (nn.n%)
DAY 1	>30 to ≤ 60	nn (nn.n%)	nn (nn.n%)
	>60	nn (nn.n%)	nn (nn.n%)
Etc...			

Baseline is defined as: Visit 2 in the MIV-711-201 for Group A, Visit 8 in the MIV-711-201 for Group B

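### Group B's ECG change categories (including rises over 60 ms) and two change listings use a different baseline visit from the one SAP Section 9 sets for safety

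*SAP*

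**What the plan says.** SAP Section 9 (Safety Analysis) takes Group A's baseline from Visit 2 of MIV-711-201 and then states: "For study Group B, changes from baseline will be assessed using the Visit 2 data from Study MIV-711-202". Section 9.4 asks for mean change and categorical change in QT, QTcB and QTcF and names no other baseline.

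The default in SAP Section 6, unless stated otherwise, is that "the baseline assessment to be used for calculating change from baseline will be the last valid assessment prior to first dose" of 200 mg MIV-711.

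The shell footnotes in SAP Sections 14 and 15 split:

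- Tables 14.3.4.1 (ECG mean change) and 14.3.3 (vital-signs mean change), and the laboratory shift tables: "Visit 2 in the MIV-711-201 for Group A, Visit 2 in the MIV-711-202 for Group B".
- Table 14.3.4.3 (ECG categorical change, with a row above 60 ms) and Listings 16.2.8.9 and 16.2.8.6: "Visit 2 in the MIV-711-201 for Group A, Visit 8 in the MIV-711-201 for Group B".

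On ECG timing, Protocol 7.7 says: "12-lead serial ECGs will be recorded at Visit 2 (Enrolment) pre-dosing and after 30 minutes", with further recordings at 1 and 2 hours. SAP 4.1, footnote C, gives the MIV-711-201 schedule: "At Visit 2 at pre-dosing, 0.5, 1 and 2 hours post-dosing", and 30 minutes after dosing at every other visit, Visit 8 included.

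**The concern.** Mean change, categorical change and the change listing are three views of one quantity, and a reader of the study report will expect them to agree. With two baselines for Group B they need not. The >60 ms row is the one a safety reader looks at first, and it is the row on the non-conforming reference. Table 14.3.4.1 reports the maximum change, so the report could show a Group B patient above 60 ms in one table beside a maximum below 60 ms in another, with a listing that agrees with only one of them. ECG abnormalities are among the safety endpoints in Protocol 7.1, and Protocol 7.3 makes those same endpoints the secondary endpoints for Group B.

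**Working it through.** The plan gives no figure to reproduce. The check compares the stated baselines and then works out what the difference does.

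**Step 1. Group B baseline by source.**

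| Source | Group B baseline | Agrees with Section 9 |
|---|---|---|
| SAP Section 9 text | 202 Visit 2 | – |
| Table 14.3.4.1, ECG mean change | 202 Visit 2 | yes |
| Table 14.3.4.3, ECG categorical change | 201 Visit 8 | no |
| Listing 16.2.8.9, ECG change | 201 Visit 8 | no |
| Table 14.3.3, vital-signs mean change | 202 Visit 2 | yes |
| Listing 16.2.8.6, vital-signs change | 201 Visit 8 | no |
| Tables 14.3.2.3 to 14.3.2.6, laboratory shifts | 202 Visit 2 | yes |

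The last row counts as four tables. Two are shown in full and two are described as similar. ECG: 2 of 3 outputs disagree. Vital signs: 1 of 2. Together: 3 of 5. With the laboratory tables: 3 of 5 + 4 = 3 of 9. Group A's baseline is 201 Visit 2 in every one of these sources, so only Group B is affected.

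**Step 2. Which visit do the SAP's own rules support?** Section 9 names 202 Visit 2. The Section 6 default gives the same answer, because the pre-dose ECG at 202 Visit 2 comes after 201 Visit 8 and before Group B's first 200 mg dose. SAP Section 8 does set 201 Visit 8 for Group B, but for efficacy. MRI and the questionnaires are not scheduled at 202 Visit 2 (SAP 4.2), so Visit 8 is their last assessment before 200 mg. ECG and vital signs are scheduled there, so that reason does not carry over to safety.

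**Step 3. How do the two reference ECGs differ?** 201 Visit 8 is 30 minutes after a placebo dose; the 202 Visit 2 baseline reading is pre-dose. The screening period is 10 ± 5 days (Protocol 4), so they are 10 − 5 = 5 to 10 + 5 = 15 days apart when 201 Visit 8 and 202 Visit 1 fall on the same day.

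**Step 4. Effect on one patient.** Let X be QTcF at a later visit, V8 the value at 201 Visit 8 and V2 the pre-dose value at 202 Visit 2.

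- Change in Table 14.3.4.3 and Listing 16.2.8.9: X − V8
- Change behind Table 14.3.4.1: X − V2
- Difference: (X − V8) − (X − V2) = V2 − V8

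The difference is the same at every later visit of that patient. The same algebra applies to blood pressure and heart rate in Listing 16.2.8.6 against Table 14.3.3.

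**Step 5. Illustration with assumed values, not taken from the documents.** Take V8 = 400, V2 = 410 and X = 465 ms. Table 14.3.4.3 sees 465 − 400 = +65 and counts the patient above 60 ms. Table 14.3.4.1 uses 465 − 410 = +55. With V2 below V8 the discrepancy runs the other way.

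**Step 6. Number of patients affected.** This cannot be computed. It needs the distribution of V2 − V8 and the number in Group B. The documents give no QTcF variability, and only an expected 50 to 80 patients for both groups together.

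**The case against.** The strongest reply is that this is copied boilerplate and not a choice. The Visit 8 footnote is Group B's efficacy baseline and runs through the change listings. It even appears on the biomarker listing (16.2.6.23), where Sections 8 and 8.3.8 set 202 Visit 2. A programmer working from Section 9 might never apply it. Listing 16.2.8.8 also prints raw QTcF by visit and time point, so either change can be recomputed. That is fair as to cause and mitigation, but shells are programming specifications, and three of them conflict with the text.

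A second reply is that 201 Visit 8 is a defensible ECG reference for Group B: it is drug-free, and it matches the on-treatment timing in Protocol 7.7 ("On dosing days, ECG should be performed 30 minutes after dosing"). That stands as an argument about design. The SAP does not make it, however, and it would not explain why the mean-change table uses the other visit.

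A reader might also infer something stronger from Protocol 5.3, which requires removal on a confirmed QTcF "increase > 60 ms from time matched baseline". Since none of Population A's 30-minute post-dose ECGs before 202 Visit 3 is drug-free, the rule might seem to force an on-drug reference. The documents do not support this. The phrase is undefined, and it could mean matching by clock time, as dosing is in the morning. For Group B the 30-minute placebo ECGs at 201 Visits 2 to 8 would also fit. Nothing shows that sites used different references.

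**Conclusion.** The SAP is wrong as written: one safety baseline is defined for Group B, and three safety outputs depart from it without explanation. The consequence is that the >60 ms counts and the listed changes will not match the mean-change tables. The effect is probably small. The outputs are descriptive, both candidate references precede any MIV-711 in Group B, Group A is untouched, and Protocol 2.2 reports no clinically meaningful QTcF effect in Phase I. That last point bears on the clinical stakes, not on how many patients would be reclassified, which remains unknown.

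Two assumptions are involved. Programming is assumed to follow the footnotes as printed. Taking the pre-dose recording as the Visit 2 baseline relies on the Section 6 default, because Section 9 names the visit but not which of its serial ECGs to use. The missing definition in Protocol 5.3 is a separate point of wording; it does not add weight to this one.

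**What to change.** In Table 14.3.4.3 and Listings 16.2.8.9 and 16.2.8.6, change the Group B baseline in the footnote to Visit 2 of MIV-711-202. Add one sentence to SAP 9.4: the ECG baseline is the pre-dose ECG at Visit 2 of MIV-711-201 for Group A and at Visit 2 of MIV-711-202 for Group B, in all ECG tables and listings. The cost is three footnotes and one sentence. Both ECGs are already scheduled, and no new table is needed.

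If 201 Visit 8 is really wanted for the categorical table, the SAP should say so, give the reason, and present mean change on the same reference.

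Separately, Protocol 5.3 could name its reference ECG. A rule triggered by a rise over either of two pre-dose ECGs is not recommended. It would make the lower of two readings decisive, add false triggers for mandatory removal, and fail to match a >60 ms table built on a single baseline.
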